- Organize a specific interview with the patient and a Registered Dietician or other qualified nutrition professional and to reinforce on the absolute need to be compliant to diet and lifestyle recommendations, and schedule an FPG/HbA1c assessment at the next visit.

If none of the above mentioned reasons can be found, or if appropriate action fails to decrease FPG/HbA1c under the threshold values, rescue medication may be introduced (18).

- Open label rescue medication(s) to treat hyperglycemia must be in accordance with local standard of care and prescribing practice for patients with CKD and will be at the discretion of the investigator. Except for SGLT2 inhibitors and medications with specific contraindications in renal impairment, any approved medication(s) including oral antidiabetic drugs or insulin can be considered with appropriate dose modification as indicated.
- The patient continues the IMP (blinded) and stays in the study in order to collect efficacy and safety information. The planned visits and assessments should occur until the last scheduled visit.
- Rescue therapy is considered an NIMP. Rescue therapy is to be reported in the e-CRF. This information should include specific drug name, dose, route of administration, and frequency.

If not covered by health insurance, the cost of rescue therapy will be reimbursed where permitted by local regulations.

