### **8.8.2 Concomitant diabetes therapy**

Any background antidiabetic therapy (oral or injected including insulin) is permitted with the exception of other SGLT2 inhibitors.

The rescue medication(s) that will be used to treat hyperglycemia (see [Section 8.2.1](#)) when a patient's hyperglycemia reaches the rescue threshold is also defined as NIMPs. Except for SGLT2 inhibitors and medications with specific contraindications in renal impairment, any approved medication(s) including oral/subcutaneous antidiabetic drugs or insulin can be prescribed to treat the hyperglycemia as long as it is used within labeling guidelines for renal impairment. In addition, for patients already prescribed insulin the dose may be increased. If a patient requires glycemic rescue, the IMP received during the randomized, double-blind Treatment Period and Extension Period should continue and must remain blinded until the end of the study. Background medication may need to be adjusted if hypoglycemia occurs.

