### **Observation period of safety endpoints**

The observation period of safety data will be divided into 3 segments:

- The pre-Treatment Period is defined as the time between the date of the informed consent and the first dose of double-blind IMP
- The on-Treatment Period (TEAE period) is defined as the time from the first dose of double-blind IMP up to 10 days (1 day for hypoglycemia) after the last dose of double-blind IMP, regardless of the introduction of rescue therapy. The 10-day interval is chosen based on the half-life of the IMP (approximately 5 times the half-life of sotagliflozin) in patients with moderate renal dysfunction
- The post-Treatment Period is defined as the time starting 11 days after the last dose of double-blind IMP (after the on-Treatment Period).

The Baseline value for safety endpoints in the safety population is the last available value (or the average of all values for creatinine or eGFR) prior to the first administration of the double-blind IMP.

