2.1.2.1 Rescue therapy

Open label rescue medication(s) to treat hyperglycemia must be in accordance with local standard of care and prescribing practice for patients with CKD and will be at the discretion of the Investigator. Except for SGLT2 inhibitors and medications with specific contraindications in renal impairment, any approved medication(s) including oral antidiabetic drugs or insulin can be considered with appropriate dose modification as indicated. Rescue therapy is considered as a non-investigational medicinal product (NIMP).

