2.1.4 Safety endpoints

The safety analysis will be based on the reported adverse events, hypoglycemia, acute renal failure, and other safety information, such as clinical laboratory data, vital signs, electrocardiogram (ECG), bone mineral density (BMD) results, physical examination, and marker of intestinal transit and absorption, markers of bone and calcium metabolism, etc.

Observation period

The observation period will be divided into 4 epochs:

- The **screening** epoch is defined as the time from the signed informed consent date up to the first administration of the double-blind IMP.
- The **treatment** epoch is defined as the time from the first administration of the double-blind IMP to the last administration of the double-blind IMP. This epoch includes the 26-week double-blind core treatment period and the 26-week double-blind extension treatment period. The 26-week core treatment period is the time from the first administration of double-blind IMP to the last administration of double-blind IMP on or before Visit 9/Week 26 (or Day 182 if Visit 9/Week 26 date is missing).
- The **residual treatment** epoch is defined as the time from the last administration of the double-blind IMP up to 10 days (1 day for hypoglycemia) after the last administration of the double-blind IMP.

The treatment-emergent adverse event (TEAE) period will include both **treatment** and **residual treatment** epochs (See TEAE period for the 26-week core treatment period in [Section 2.5.4](#)).

- The **posttreatment** epoch is defined as the period of time starting the day after the end of the treatment-emergent adverse event period up to the last protocol-planned visit or the

resolution/stabilization of all serious adverse events (SAE), adverse events of special interest (AESI) and events of special interest (EOSI), whichever is later.

The on-study observation period is defined as the time from start of double-blind treatment until the end of the study (defined as the last scheduled visit for those who completed the study and the date collected on e-CRF page “Completion of End of Study/Follow-up” for those who did not complete the study).

The post-study observation period is defined as the time from the day after the end of the study until the resolution/stabilization of all SAE, AESI and EOSI if applicable.

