The adjusted estimates of treatment mean difference (each sotagliflozin group versus placebo) with standard error (SE) and 95% CIs will be provided as appropriate across the subgroups. A forest plot of the results will also be presented.

In the case that the subgroup factor is identical or similar to the randomization strata (eg, baseline HbA1c or baseline mean SBP category), only the subgroup factor (as a single factor or an interaction term) will be included in the model in order to avoid the issue of collinearity in the analysis. The corresponding strata factor will not be included in the model.

Summary statistics at scheduled visits

Summary statistics (for screening value, baseline value, observed post-baseline value and its changes from baseline) at scheduled visits will be provided for each treatment group. The summary will include the number of observations, mean, SD, SE, minimum, median, and maximum. Graphical presentations will also be used to examine trends over time using mean values (\pm SE) and mean changes from baseline (\pm SE) at each of the scheduled visits.

Similar presentations will be provided excluding measurements after rescue therapy during the entire 52-week double-blind treatment period.

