2.4.5.1 Analyses of hypoglycemia

Analyses of hypoglycemia will be performed on the TEAE period as defined in [Section 2.1.4](#). Hypoglycemia will be classified as severe hypoglycemia, documented symptomatic hypoglycemia, asymptomatic hypoglycemia, probable symptomatic hypoglycemia or relative hypoglycemia (See [Section 2.1.4.1](#)).

The number (%) of patients with 1) any hypoglycemia, 2) severe hypoglycemia and documented symptomatic hypoglycemia will be summarized respectively by treatment group during the TEAE period, as well as the incidence rate in patient years. Two types of incidence rates will be presented: the number of patients with event(s) per 100 patient-years (calculated as the number of patients with at least 1 event/ total exposure in 100 patient-years) and the total number of events per 100 patient-years (calculated as the total number of events / total exposure in 100 patient-years). Note: here exposure in days is duration of treatment-emergent AE period, ie, duration of IMP treatment in days +1 ([Section 2.1.4](#)).

The summary of frequency and incidence rate in patient-years for severe hypoglycemia or documented symptomatic hypoglycemia will be provided as appropriate by gender, age group (<50, ≥50 to <65, ≥65 years), race (White, Black or African American, Asian, Other), baseline eGFR category, prior antidiabetic medication (No antidiabetic therapy, Insulin [alone or with other antihyperglycemic agents], SU and/or glinide [alone or with other non-insulin antihyperglycemic agents], Other [non-insulin antihyperglycemic agents except SU and glinide]).

A KM curve will be provided by treatment group for the time to first severe hypoglycemia or documented symptomatic hypoglycemia during the TEAE period for the 52-week entire treatment period only (see [Section 2.5.4](#)).

Documented symptomatic hypoglycemia may be presented by ≤ 70 mg/dL (3.9 mmol/L) and < 54 mg/dL (3.0 mmol/L) respectively, as appropriate.

A listing of patients for all events reported on the dedicated e-CRF “Hypoglycemic event information” page will be provided with each category flagged (ie, severe hypoglycemia, documented symptomatic hypoglycemia, asymptomatic hypoglycemia, probable symptomatic hypoglycemia and relative hypoglycemia).

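### Every planned hypoglycemia summary includes time after glycemic rescue, so the arm comparison can understate a drug-related excess; a supplementary pre-rescue analysis would be a cheap improvement

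*SAP*

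**What the plan says.** The hypoglycemia section of the SAP (2.4.5.1) opens with "Analyses of hypoglycemia will be performed on the TEAE period as defined in" Section 2.1.4. The SAP ends that period by study-drug dosing alone: "up to 10 days (1 day for hypoglycemia) after the last administration of the double-blind IMP". Protocol 9.2 makes the treatment of rescue explicit: "up to 10 days (1 day for hypoglycemia) after the last dose of double-blind IMP, regardless of the introduction of rescue therapy".

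The rate denominators match: "here exposure in days is duration of treatment-emergent AE period, ie, duration of IMP treatment in days +1". For the 52-week Kaplan-Meier curve, SAP Table 5 censors at the earlier of end of treatment plus one day and end of study. Rescue is not a censoring event. The subgroup tables use prior antidiabetic medication, not rescue medication.

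On rescue itself, SAP 2.1.2.1 says that "any approved medication(s) including oral antidiabetic drugs or insulin can be considered with appropriate dose modification as indicated", and Protocol 8.8.2 adds that "for patients already prescribed insulin the dose may be increased". After rescue, "The patient continues the IMP (blinded) and stays in the study" (Protocol 8.2.1), so post-rescue time remains in the hypoglycemia analysis.

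For HbA1c the SAP does plan a second view (2.4.4.1): "Similar presentations will be provided excluding measurements after rescue therapy during the entire 52-week double-blind treatment period". Neither 2.4.5.1, Table 5 nor Appendix D has a counterpart for hypoglycemia.

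**The concern.** Rescue is triggered by poor glycemic control, and several of the permitted rescue drugs can themselves cause hypoglycemia. If the study drug works, more placebo patients cross the rescue thresholds, and placebo person-time then carries more hypoglycemia caused by rescue. The planned rates would combine two effects: that of sotagliflozin and that of unequal rescue. The second pulls the sotagliflozin-to-placebo ratio down.

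Severe hypoglycemia is an event of special interest in this trial, and Protocol 10.4.2 itself warns that concomitant antidiabetic drugs complicate causal assessment of hypoglycemia in particular. A reader who wants to know whether adding sotagliflozin to existing therapy raises hypoglycemia would have no planned table that separates the two effects.

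**Working it through.** **1. The plan's own figures.** The documents state no rescue rate, hypoglycemia rate or effect of rescue on hypoglycemia. The nearest stated figures are the HbA1c power values in SAP 1.3, which supply the effect sizes used in step 2. With power = Φ(d / (SD × √(2/n)) − 1.96) and SD 1.2:
- 400 mg, d = 0.6: 0.981 with n = 130 and 0.9999 with n = 260 (stated 98% and 99%).
- 200 mg, d = 0.5: 0.919 with n = 130 and 0.997 with n = 260 (stated 91% and 99%).
- All six tests, by simulation: 0.825 (stated at least 80%).

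The stated figures reproduce.

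**2. Direction of the rescue imbalance.** From Week 12 the HbA1c rescue criterion is 8.5% or more. Take HbA1c as normal with SD 1.2 (the plan's SD for change, used here for the level, which is an assumption) and assume a placebo mean of 7.8% to 8.5%. Then the share at or above 8.5% = 1 − Φ((8.5 − mean)/1.2):
- Placebo: 28% to 50%.
- 200 mg (mean lower by 0.5): 16% to 34%.
- 400 mg (mean lower by 0.6): 14% to 31%.

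These are not rescue rates, because rescue also needs a confirmatory re-test and exclusion of other causes. They show only the direction. The exemption for patients whose HbA1c has fallen by 1.0% or more, ignored here, would widen the gap.

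**3. Size of the bias, under assumed inputs.** Let r_p and r_s be the proportions rescued on placebo and sotagliflozin, half of a rescued patient's follow-up fall after rescue, and m be the multiplier on the event rate after rescue.

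Observed ratio = true ratio × [1 + 0.5 r_s (m − 1)] / [1 + 0.5 r_p (m − 1)]

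| True ratio | r_p, r_s | m = 2 | m = 3 |
|---|---|---|---|
| 1.20 | 20%, 8% | 1.20 × 1.04/1.10 = 1.13 | 1.20 × 1.08/1.20 = 1.08 |
| 1.20 | 30%, 12% | 1.20 × 1.06/1.15 = 1.11 | 1.20 × 1.12/1.30 = 1.03 |
| 1.50 | 20%, 8% | 1.42 | 1.35 |
| 1.50 | 30%, 12% | 1.38 | 1.29 |

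With m = 1 the observed ratio equals the true ratio. The formula applies to the total event rate. The same mechanism acts on the percentage of patients with an event and on time to first event, but these figures do not measure it there.

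**4. Is half of follow-up after rescue reasonable?** In the 52-week table it corresponds to rescue at Week 26 (26/52). In the 26-week table it is close to the maximum for HbA1c-triggered rescue, since rescue at Week 12 leaves 14/26 = 54%. Rescue at Week 18 leaves 8/26 = 31%; with 20% and 8% rescued and m = 2, a true 1.20 is then seen as 1.20 × 1.025/1.062 = 1.16.

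**5. Is the pre-rescue ratio unbiased?** No, if rescued patients differ in prior risk. Take 30% and 12% rescued and a true ratio of 1.20. Suppose rescued patients have half the prior hypoglycemia rate of the others, and scale both arms to the same average prior rate: 0.70 + 0.30 × 0.5 = 0.85 on placebo and 0.88 + 0.12 × 0.5 = 0.94 on sotagliflozin.
- Planned, m = 2: placebo (0.70 + 0.15 × 1.5)/0.85 = 1.088; sotagliflozin (0.88 + 0.06 × 1.5)/0.94 = 1.032; ratio 1.20 × 1.032/1.088 = 1.14.
- Planned, m = 3: 1.00/0.85 = 1.176 and 1.00/0.94 = 1.064; ratio 1.09.
- Pre-rescue: placebo (0.775/0.85)/0.85 = 1.073; sotagliflozin (0.91/0.94)/0.94 = 1.030; ratio 1.15.

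Here the pre-rescue ratio is nearer to 1.20 than the planned one, but it is not 1.20.

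**The case against.** The strongest reply is that this is a deliberate choice. The protocol says in terms that the on-treatment period ignores rescue. That is a coherent treatment-policy view of safety: it describes what happens to patients assigned to each arm, rescue included. This stands, and the planned tables should not be replaced.

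Second, other outputs would reveal part of the problem. Appendix D plans hypoglycemia by weekly interval, a 26-week summary is planned, and rescue use and time to rescue are shown by arm. Before Week 12 rescue depends on high fasting glucose thresholds alone, so early intervals may be largely free of rescue. This helps a careful reader. None of these outputs, however, gives events over pre-rescue person-time by arm, and the 26-week table also runs through rescue.

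Third, stopping at rescue has its own bias. Rescued patients are hyperglycemic and may be at lower prior risk, so removing their later time, mainly from placebo, raises the remaining placebo rate. Step 5 of the working confirms this. It is the reason not to rest the arm comparison on pre-rescue figures alone.

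Fourth, safety is descriptive and relative risks are optional (SAP 2.4.5). True, but arm-by-arm rates still inform the safety conclusion.

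A reader might infer that the plan does mask an excess, or turns it into an apparent benefit. The documents do not support either. Masking requires rescue rates and a post-rescue multiplier that they do not give, and no scenario in the table falls below 1. In a wider grid a true 1.20 falls below 1 only with 20% of placebo and 10% of sotagliflozin person-time after rescue and a fivefold rate (0.93), or with 30% and 15% and at least a tripled rate (0.975 when tripled). At half of follow-up after rescue, 20% of person-time means 40% of placebo patients rescued.

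**Conclusion.** The point holds as a cheap improvement. All hypoglycemia counts, rates and the Kaplan-Meier curve in SAP 2.4.5.1 include post-rescue time, rescue may itself lower glucose strongly, and no pre-rescue view is planned. The comparison can therefore understate a drug-related excess. Under the stated assumptions a true event-rate ratio of 1.20 is seen as 1.03 to 1.13, and a true 1.50 as 1.29 to 1.42. The direction rests on two conditions: that sotagliflozin lowers HbA1c roughly as the sample-size section assumes, and that rescue raises hypoglycemia. If the second fails, rescue introduces no such bias. The gap is a missing companion analysis, not an error in the planned one.

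**What to change.** Keep the regardless-of-rescue tables as planned. Add to SAP 2.4.5.1 and Table 5 a supplementary pre-rescue analysis by arm for any, severe and documented symptomatic hypoglycemia:
- Count events and person-time from first dose to the earlier of first rescue and last dose plus one day.
- Present the Kaplan-Meier curve also with censoring at first rescue.
- State in advance that the two views are read together, with the pre-rescue figures supportive and not the sole basis for the comparison.

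The cost is a little programming. Rescue is flagged in the e-CRF (SAP 2.1.3) and time to first rescue is already planned (SAP 2.4.4.3), so no new data are needed; nothing is tested, so the type I error plan is unaffected. The drawbacks are less person-time, chiefly on placebo, and informative censoring at rescue, which should be acknowledged beside the table.

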### **10.6.1 Hypoglycemia**

During the study, patients are instructed to document any hypoglycemic episodes in their study diary. The hypoglycemia will be reported in the specific e-CRF page with onset date and time, symptoms and/or signs, the SMBG value if available, and the treatment. If the event fulfills SAE criteria, hypoglycemia will also be reported as an SAE.

Hypoglycemia is categorized according to the ADA workgroup on hypoglycemia classification (19)(20) and summarized in [Figure 1](#).

In addition of the threshold of less than or equal to 70 mg/dL (3.9 mmol/L), hypoglycemia episodes with a plasma glucose of <54 mg/dL (3.0 mmol/L) will be analyzed separately.

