2.1.4.1 Hypoglycemia

Hypoglycemia will be identified as events recorded on the dedicated e-CRF “Hypoglycemic event information” page, and will be categorized as follows (see study protocol for further details):

Severe hypoglycemia

Severe hypoglycemia is an event requiring assistance of another person to actively administer carbohydrate, glucagon, intravenous glucose or other resuscitative actions. These episodes may be associated with sufficient neuroglycopenia to induce seizure, unconsciousness or coma.

Self-monitored plasma glucose values may not be available, but neurological recovery attributable to the restoration of plasma glucose to normal is considered sufficient evidence that the event was induced by a low plasma glucose concentration.

Severe hypoglycemia is identified in e-CRF “Hypoglycemic Event Information” page as those documented as,

1. To the question “Countermeasure Administration”, ticked the option “Subject was Not Capable of Treating Self and Required Assistance”, and
2. To the question “Were Symptoms Present”, ticked “Yes”.

Documented symptomatic hypoglycemia

Documented symptomatic hypoglycemia is an event during which typical symptoms of hypoglycemia accompanied by a measured plasma glucose concentration of ≤ 3.9 mmol/L (≤ 70 mg/dL).

Clinical symptoms that are considered to result from a hypoglycemic episode include increased sweating, nervousness, asthenia/weakness, tremor, dizziness, increased appetite, palpitations, headache, sleep disorder, confusion, seizures, unconsciousness, or coma.

Documented symptomatic hypoglycemia is identified in e-CRF “Hypoglycemic Event Information” page as those documented as,

1. To the question “Countermeasure Administration”, NOT ticked the option “Subject was Not Capable of Treating Self and Required Assistance”, and
2. To the question “Were Symptoms Present”, ticked “Yes”, and
3. With a plasma glucose value before countermeasure ≤ 3.9 mmol/L (≤ 70 mg/dL).

Asymptomatic hypoglycemia

Asymptomatic hypoglycemia is an event not accompanied by typical symptoms of hypoglycemia but with a measured plasma glucose concentration ≤ 3.9 mmol/L (≤ 70 mg/dL).

Asymptomatic hypoglycemia is identified in e-CRF “Hypoglycemic Event Information” page as those documented as,

1. To the question “Countermeasure Administration”, NOT ticked the option “Subject was Not Capable of Treating Self and Required Assistance”, and
2. To the question “Were Symptoms Present”, ticked “No”, and

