3. With a plasma glucose value before countermeasure ≤ 3.9 mmol/L (≤ 70 mg/dL).

Probable symptomatic hypoglycemia

Probable symptomatic hypoglycemia is an event during which symptoms of hypoglycemia are not accompanied by a plasma glucose determination, (but that was presumably caused by a plasma glucose concentration ≤ 3.9 mmol/L [≤ 70 mg/dL]), ie, symptoms treated with oral carbohydrate without a test of plasma glucose.

Probable symptomatic hypoglycemia is identified in e-CRF “Hypoglycemic Event Information” page as those documented as,

1. To the question “Countermeasure Administration”, NOT ticked the option “Subject was Not Capable of Treating Self and Required Assistance”, and
2. To the question “Were Symptoms Present”, ticked “Yes”, and
3. With no plasma glucose value before countermeasure, and
4. To the question “Did this countermeasure lead a significant improvement or prompt recovery”, ticked “Yes”.

Relative hypoglycemia

Relative hypoglycemia, recently termed “pseudo-hypoglycemia”, is an event during which the patient reports typical symptoms of hypoglycemia, and interprets the symptoms as indicative of hypoglycemia, but with a measured plasma glucose concentration > 3.9 mmol/L (> 70 mg/dL).

Relative hypoglycemia is identified in e-CRF “Hypoglycemic Event Information” page as those documented as,

1. To the question “Countermeasure Administration”, NOT ticked the option “Subject was Not Capable of Treating Self and Required Assistance”, and
2. To the question “Were Symptoms Present”, ticked “Yes”, and
3. With a plasma glucose value before countermeasure > 3.9 mmol/L (> 70 mg/dL).

In addition of the threshold of ≤ 3.9 mmol/L (≤ 70 mg/dL), hypoglycemia episodes with plasma glucose of < 3.0 mmol/L (< 54 mg/dL) will be analyzed separately.

Any hypoglycemic event fulfilling the criteria of a SAE or leading to unconsciousness, coma, or seizure will also be recorded as a SAE (see [Section 2.1.4.2](#)).

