Hypoglycemia	Safety	Follow safety guidelines Number (%) of patients with any investigator reported hypoglycemia, severe hypoglycemia, documented symptomatic hypoglycemia during TEAE period, and incidence rates in 100 patient-years.		Severe hypoglycemia or documented symptomatic hypoglycemia by subgroups: race, age group, gender	Severe hypoglycemia or documented symptomatic hypoglycemia: frequency summary of first event/recurrent event by weekly time intervals; frequency summary of any event by hour; KM plot time to first event Documented symptomatic hypoglycemia maybe presented by <54 mg/dL (3.0 mmol/L) as appropriate
Adverse events	Safety	Follow safety guidelines	No	Common TEAEs by subgroups: race, age, gender, baseline SBP, baseline eGFR	To be updated for EOSI
Clinical laboratory data	Safety	Follow safety guidelines	Descriptive	No	No
Vital signs	Safety	Follow safety guidelines	Descriptive	No	No
ECG, Physical examination	Safety	Follow safety guidelines	Frequency summary	No	No

Statistical Analysis Plan

Version: Final 3.0

Lexicon Pharmaceuticals Protocol No. EFC14837

Date of Issue: 21 November 2019

Covance Study ID:000000155205

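### The analysis of hypoglycemia below 54 mg/dL is promised without restriction by category, but the SAP's analysis section makes it optional and limits it to documented symptomatic events

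*SAP*

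**What the plan says.** Protocol 10.6.1, after introducing the 70 mg/dL threshold, states that "hypoglycemia episodes with a plasma glucose of <54 mg/dL (3.0 mmol/L) will be analyzed separately". SAP 2.1.4.1 repeats the commitment once all five hypoglycemia categories have been defined: "hypoglycemia episodes with plasma glucose of < 3.0 mmol/L (< 54 mg/dL) will be analyzed separately". Neither sentence is attached to one category.

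SAP 2.4.5.1 sets out the tables. It plans patient counts and two incidence rates for any hypoglycemia and for severe and documented symptomatic hypoglycemia. It adds subgroup summaries and a Kaplan-Meier curve for severe or documented symptomatic events, and a listing of all events with their category flagged. On the lower threshold it says: "Documented symptomatic hypoglycemia may be presented by ≤ 70 mg/dL (3.9 mmol/L) and < 54 mg/dL (3.0 mmol/L) respectively, as appropriate". Appendix D has the same optional wording: "Documented symptomatic hypoglycemia maybe presented by <54 mg/dL (3.0 mmol/L) as appropriate".

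Protocol 11.4.3.2, the protocol's own analysis section, names all, severe and documented symptomatic hypoglycemia and gives no analysis at 54 mg/dL.

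**The concern.** The commitment changes in two ways between the section that makes it and the section that carries it out. It goes from *will* to *may*, and from hypoglycemia episodes in general to the documented symptomatic category.

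Hypoglycemia is a named safety endpoint (Protocol 9.2), and severe hypoglycemia is an event of special interest. Background insulin is permitted, and Protocol 4.5 itself refers to the longer half-life of insulin when renal function is reduced. Fasting self-monitoring at least three times a week, with values of 70 mg/dL or less entered in the diary (Protocol 9.2.1.8), means that low readings without symptoms can be captured. At stake is whether the report will show, by arm, how often glucose fell below 54 mg/dL, or only how often it did so with symptoms and without assistance.

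**Working it through.** There is no plan figure to reproduce. The check is a comparison of the texts, in three steps.

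**Step 1. Which categories can hold a value below 54 mg/dL?** From the algorithm in SAP 2.1.4.1:

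| Category | Assistance option ticked | Symptoms | Glucose condition | Can hold a value <54 mg/dL |
|---|---|---|---|---|
| Severe | Yes | Yes | None; a value may be absent | Yes, if a value was recorded |
| Documented symptomatic | No | Yes | ≤70 mg/dL | Yes |
| Asymptomatic | No | No | ≤70 mg/dL | Yes |
| Probable symptomatic | No | Yes | No value | No |
| Relative | No | Yes | >70 mg/dL | No |

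The three that can are mutually exclusive. Documented symptomatic requires the assistance option to be "NOT ticked the option", which rules out severe events, and it requires symptoms, which rules out the asymptomatic category. The latter has no lower glucose bound: "Asymptomatic hypoglycemia is an event not accompanied by typical symptoms of hypoglycemia but with a measured plasma glucose concentration" at or below 70 mg/dL.

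**Step 2. Which of the three have a planned summary at 54 mg/dL?** Under 2.4.5.1 and Appendix D, one of three: documented symptomatic, and that one as an option. Severe and asymptomatic have none.

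**Step 3. Does anything else recover them?**

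- The row for any hypoglycemia includes all categories but is not cut at 54 mg/dL.
- The row for severe hypoglycemia is not cut by glucose.
- Asymptomatic hypoglycemia has no row of its own in 2.4.5.1.
- The listing is specified with a flag for category, not for glucose level. It is not a summary by arm.
- SAP 2.4.5 excludes plasma glucose from the summaries of potentially clinically significant abnormalities. The low-glucose criterion in Appendix A is 3.9 mmol/L or less, not 3.0 mmol/L.

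So the commitment in Protocol 10.6.1 and SAP 2.1.4.1 has no analysis rule of matching scope.

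**The case against.** Several points on the other side are sound.

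- A reader might infer that asymptomatic and severe episodes disappear from the safety report. They do not. Severe events are always tabulated, appear in the Kaplan-Meier curve and are events of special interest. Both types count under any hypoglycemia, and both are listed.
- A reader might infer that the documents promise all episodes in so many words. They do not use that word. They refer to episodes below the threshold without a category limit.
- A reader might infer that the *may* in 2.4.5.1 cancels the analysis. It does not: SAP 2.1.4.1 is current text in the same version, and "will be analyzed separately" still stands there. The two sections conflict, and neither is said to govern.
- The case for severe events is weaker than for asymptomatic ones. The 54 mg/dL cut is introduced alongside the 70 mg/dL threshold, whereas severe events are defined by assistance and may have no glucose value.
- Protocol 10.6.1 warns that low readings without symptoms can reflect a faulty device or a testing error. That is a fair reason to show documented symptomatic events on their own. It does not explain why the wider analysis, stated in both documents, is absent.
- The endpoint named in Protocol 9.2 is all, severe and/or documented symptomatic hypoglycemia, and 2.4.5.1 delivers those summaries. The 54 mg/dL cut is a stated analysis, not a listed endpoint.

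It is also tempting to size the loss by assuming a share of episodes that are symptom-free or assisted, and to turn that into lost precision of a rate ratio. The documents give no such share. The plan specifies no rate ratio for hypoglycemia, and SAP 2.4.5 describes the safety analyses as essentially descriptive.

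**Conclusion.** The concern holds as a conflict between a stated commitment and the rule that produces the tables. Followed as written, SAP 2.4.5.1 leaves asymptomatic episodes below 54 mg/dL, and assisted episodes with a recorded value below 54 mg/dL, out of any summary by arm at that threshold. The documented symptomatic presentation itself is discretionary. The size is structural: two of the three categories that can hold such values have no summary at that cut, and the third has an optional one. How many episodes this affects cannot be derived from the documents.

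The conclusion rests on reading the sentences in Protocol 10.6.1 and SAP 2.1.4.1 as applying across categories. Their wording and, in the SAP, their position after all five definitions support that reading. No efficacy conclusion or error rate is affected.

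One circumstance favors closing the option. SAP 1.6 says the first step analysis was conducted and reported for top line results, and SAP Section 3 lists interim safety analyses within that step. A reader might infer that the option was left open with results by arm in view. The documents do not say so. The visible change tables do not record the narrowing, but some of their rows are redacted, so nothing follows from that. The point is only that a discretionary safety table is better fixed in advance.

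**What to change.** In SAP 2.4.5.1 and Appendix D, replace the optional sentence with a commitment. Present the number (%) of patients and the events per 100 patient-years, by treatment group, for any episode with measured plasma glucose below 54 mg/dL (3.0 mmol/L), regardless of symptoms or assistance. Show the documented symptomatic subset as a second row, so that a reader wary of symptom-free readings can see it separately. This brings both places into line with SAP 2.1.4.1 and Protocol 10.6.1. If the narrower analysis is what is intended, the SAP should say so, give the reason, record it as a change from the protocol, and amend 2.1.4.1 to match.

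The cost is a sentence in each of two places and one or two descriptive rows. The category items and, where available, the glucose value are already on the hypoglycemia e-CRF page. The count reported below 54 mg/dL will be higher wherever symptom-free or assisted episodes at that level occurred.
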